1.0 Introduction

1.1 Study Conduct

This study will be conducted in compliance with the protocol approved by the Institutional Review Board (IRB), and according to Good Clinical Practice standards. No deviation from the protocol will be implemented without the prior review and approval of the IRB except where it may be necessary to eliminate an immediate hazard to a research subject. In such case, the deviation will be reported to the IRB according to its policies and procedures.

1.2 Background

Despite many advances in imaging and therapy, prostate cancer remains the second most common cause of cancer-related death of men in the United States (1). Over one million men undergo prostate biopsies annually in the US. These biopsies have routinely been blind bilateral biopsies of the gland based on transrectal ultrasound guidance to assess tissue from representative section of the gland. The standard practice continues to evolve, and has progressed biopsies from unlabeled location of the right and left gland to routine biopsy of up to 12 labeled regions of the prostate including both medial and lateral locations from the base, mid, and apical regions(2, 3). By obtaining an increased number of biopsy locations, the percentage of detected cancers has been shown to increase. The potential disadvantages to increasing the number of biopsies however include increased patient discomfort and risk of complications as well as increased cost. It may also increase the number in clinically insignificant cancers that are detected, thus placing the patient at an increased risk of harm from treatment of tumors with a low risk of becoming life threatening such as low volume low grade disease (4). Most recently the introduction of MRI to guide and track biopsy location has been developing.

The use of MRI imaging has become increasingly more prevalent in the guidance of prostate biopsies both in the United States and internationally. Studies have confirmed that the use of MRI imaging to help direct the location of biopsies has increased both the frequency of diagnosing cancer, but even more importantly diagnosing clinically significant higher grade disease (5, 6). Several commercially available devices have come to market that aid in the ultrasound guidance of prostate cancer in patients that have had an MRI obtained prior to the biopsy (7). These devices may be designed for either transrectal or transperineal guided biopsy. Almost all of these manufactures have relied on the ability to use image fusion to align a real time transrectal ultrasound image of the prostate to the previously acquired MR image. By using segmentation tools to define high risk volumes likely to harbor cancer, these systems aid in the placement of a biopsy needle to the site of a suspected tumor foci. One such system, Uronav, developed by a subsidiary of Philips Medical, InVivo, has been FDA approved for routine use in transrectal guided biopsies of the prostate gland using an electromagnetic (EM) sensory system to help guide the biopsy needle tip to within 2 mm of the desired biopsy target defined by MRI. They have developed an additional version for transperineal biopsy as well and seek a validation trial to assess this platform.

Routinely all patients at University Hospitals schedule to receive prostate brachytherapy treatment undergo a 3T MR imaging of the pelvis and prostate to plan prostate brachytherapy. At the time of the brachytherapy procedure a transrectal ultrasound probe is used to image the prostate, and a commercially available computer planning system, Symphony (MIM Software, Beachwood,

Ohio) is used to align the MR image to the live ultrasound image to assist in needle placement and brachytherapy source delivery. During the procedure typically 20 to 35 needles are placed transperineally to deposit the brachytherapy sources per the computerized plan. Regions that are found to be suspicious for harboring cancer within the prostate volume are routinely planned to received a higher dose of radiation than the whole gland by placing additional radioactive sources at these locations at the time of the implant, however without a biopsy confirming the image findings it is unknown if these radiographic findings represent the biopsy proven disease site within the patients, or if these lesions may harbor higher grade disease or are false positive findings.

Hypothesis: Multiparametric MRI with histopathological correlation will improve the segmentation of the target volumes to treat sub-volumes of the prostate with focal dose escalation in low- and intermediate-risk patients beyond the use of imaging alone using standard T1 and T2 MRI and the addition of functional MRI sequences.

1.3 Preclinical Data

The use of the electromagnetic guidance system employed by Uronav was developed at the NCI. Funding was partially supplied by Philips to develop the system platform originally labeled Percunav. Non-animal phantom studies were followed by animal studies to provide the initial validation and safety profile for FDA approval in human subjects (8).

1.4 Clinical Data to Date

The NCI went on to complete a human trial using the electromagnetic guidance system to compare MRI directed biopsies versus routine sextant biopsies in a series of 101 patients with a known diagnosis of prostate cancer. The data confirmed the transrectal ultrasound guided biopsy of the fused ultrasound and MR images yielded a higher rate of positive biopsies and also increased the yield for positive biopsies of high Gleason grade disease than routine ultrasound imaging directed biopsy alone (6). Limitations for the transrectal system include difficulty in placement of biopsy needles into regions seen in the anterior gland or transitional zone, as well as the increasingly prevalent risk of post procedural infections or rectal bleeding presumably related to the transrectal needle placement (9, 10).

2.0 Study Objectives

Specific Aim 1: Evaluate final pathology post-operatively for histopathology confirmation of multiparametric MRI targets detected during treatment planning. This will be accomplished by using transperineal biopsies obtained prior to interstitial brachytherapy during the procedure, while under anesthetic just prior to the placement of the brachytherapy needles and sources.

Specific Aim 2: Evaluate the ability of the Uronav system in a transperineal setting to guide biopsy needle placement using the electromagnetic guidance system and transperineal ultrasound probe stabilization device and stepper.

3.0 Study Design

3.1 General Design

This 1-year pilot study will include 6 patients with a clinical diagnosis of prostate cancer (clinical stage T2a or T1cN0M0), Gleason score ≤ 7 (4+3), with a PSA ≤ 15 ng/mL and routine pelvic screening with MRI of the prostate and pelvis for staging and treatment planning who have elected to undergo prostate brachytherapy as definitive treatment.

Only patients who have clinically detectable intraprostatic findings on the MRI will be eligible to participate, and will be screened from the routine population of patients undergoing prostate brachytherapy at University Hospitals.

3.2 Primary Study Endpoints

The primary endpoint will be to report correlation of biopsy tissue histopathology with intraprostatic MRI findings. A total of 12 to 15 tissue samples will be obtained from each subject using standard sextant biopsies in addition to targeted biopsies of intraprostatic MRI findings. Assuming 14 specimens are sent for histopathology analysis in 6 subjects we will use the 84 biopsy sites to report sensitivity and specificity for the MRI findings along with positive and negative predictive values.

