6.0 Study Biopsy Procedures

6.1 Description biopsy procedure

All biopsies will be completed in the outpatient setting in the ambulatory OR prior to routine prostate brachytherapy under general anesthesia. Patients will be prepped in a dorsal lithotomy position with insertion of a Foley catheter. The perineum will be shaved as needed, and cleansed with antiseptic solution, and the scrotum will be elevated with a towel roll to expose the perineum. The FDA approved DynaCAD and Uronav system will be used to localize the diagnostic MRI findings within the prostate. The 510K approved tranperineal Uronav system will

be used to perform transperineal biopsy with electromagnetic alignment of the transrectal probe and stepper system attached to the perineal biopsy guide 17 gauge template.

Specimens will be sent to anatomic pathology office of:
[name] in separate cassettes at [name]
[name]
[name]

They will be received by [name], PhD.

Each specimen will be sent separately and identified by location in the prostate (1-12 a or p to identify the involved portion of the gland divided in 12 sextants and either anterior or posterior to midline of the coronal plane) along with PIRADS classification of the lesion in MRI report. The proximal and distal end of the sample will be dyed for orientation in the OR at the time of acquisition of each sample, or at a minimum noted if it is from the proximal, mid or distal 1/3 portion of the biopsy cavity to correlate with the same region of the virtual fiducial marker placed at the site of the biopsy.

Standard stains will be used to identify tumors within the specimen with photos taken after processing is completed to allow localization relative to the virtual fiducial marker placed at the site of the biopsy using the Uronav system. The pathology evaluation will be provided through [name].

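### Unweighted sensitivity and specificity over biopsied sites overstate whole-gland sensitivity and understate specificity, because extra cores are aimed at MRI findings

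*Combined protocol and SAP*

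**What the plan says.** Section 3.2 sets the yield and its source: "A total of 12 to 15 tissue samples will be obtained from each subject", obtained "using standard sextant biopsies in addition to targeted biopsies of intraprostatic MRI findings". It continues "Assuming 14 specimens are sent for histopathology analysis in 6 subjects" and concludes "we will use the 84 biopsy sites to report sensitivity and specificity for the MRI findings", together with predictive values. Section 10.1 repeats the 84 sites.

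Section 10.2 forms true and false positives and negatives from these sites and reports the four measures as binomial proportions. It gives no weight, no sampling fraction, no map from cores to parts of the gland, and no rule for MRI-negative tissue that receives no core.

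Section 6.1 labels each specimen "1-12 a or p to identify the involved portion of the gland divided in 12 sextants and either anterior or posterior to midline" and sends the lesion's PIRADS class with it. Nothing asks for the MRI status of parts of the gland without a core. Section 3.1 admits only men with an MRI finding, so every man has something to target.

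**The concern.** Sensitivity asks what share of the cancer in the gland the MRI flagged. Its denominator includes cancer in MRI-negative tissue. Here the chance that a piece of tissue gets histology depends on the MRI result, which is the test being evaluated. If MRI-positive tissue is sampled more densely, false negatives and true negatives are under-counted relative to true and false positives. Sensitivity then rises and specificity falls, whatever the number of patients.

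This is the primary endpoint. The hypothesis in section 1.2 concerns defining sub-volumes for focal dose escalation, and section 4.1 looks ahead to therapeutic trials built on these correlations. For that use, the amount of cancer outside the MRI targets matters a great deal, and that is the cancer the planned count under-represents.

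**Working it through.** **The plan's own count.** 14 specimens × 6 men = 84 sites, as stated. The 12 to 15 range gives 72 to 90. The 82% power in section 10.1 is a separate calculation and is not affected by this point.

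**General form.** Let S and Sp be whole-gland sensitivity and specificity, and r the sampling density of MRI-negative tissue divided by that of MRI-positive tissue. The unweighted values are

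- sensitivity = S / (S + (1 − S)·r)
- specificity = Sp·r / (Sp·r + 1 − Sp)

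With r = 1 there is no bias. Targeted cores added to a systematic set make r < 1.

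**Reading A: 24 sectors, one core each, all MRI-positive sectors sampled.** 12 numbered portions × anterior/posterior = 24. With 12 to 15 cores, 12 to 9 sectors have no core (50% to 37.5%; 10 of 24, or 42%, at 14 cores). All of these are MRI-negative.

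Illustration with assumed rates: 14 cores, 2 MRI-positive sectors per man, PPV 60%, cancer in 10% of MRI-negative sectors. Then 14 − 2 = 12 of the 24 − 2 = 22 MRI-negative sectors are sampled, so r = 12/22 = 0.545.

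| Per man | All 24 sectors | Sampled sites |
|---|---|---|
| TP | 2 × 0.6 = 1.2 | 1.2 |
| FP | 2 × 0.4 = 0.8 | 0.8 |
| FN | 22 × 0.1 = 2.2 | 12 × 0.1 = 1.2 |
| TN | 22 × 0.9 = 19.8 | 12 × 0.9 = 10.8 |
| Sensitivity | 1.2/3.4 = 35% | 1.2/2.4 = 50% |
| Specificity | 19.8/20.6 = 96% | 10.8/11.6 = 93% |
| PPV | 60% | 60% |
| NPV | 90% | 90% |

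Weighting the sampled MRI-negative sectors by 22/12 = 1.83 restores FN = 2.2 and TN = 19.8, and so the whole-gland values.

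**Range under reading A.** The grid is 1 to 3 MRI-positive sectors, PPV 40% to 80%, and 5% to 15% cancer in MRI-negative sectors. All three are assumptions.

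- 14 cores, smallest: 1 sector, 40%, 15%. 0.4/(0.4 + 3.45) = 10.4% becomes 0.4/(0.4 + 1.95) = 17.0%, or 6.6 points.
- 14 cores, largest: 3 sectors, 50%, 10%. 1.5/(1.5 + 2.1) = 41.7% becomes 1.5/(1.5 + 1.1) = 57.7%, or 16.0 points.
- 12 to 15 cores, smallest: 15 cores, 1 sector, 40%, 15%. 10.4% becomes 0.4/(0.4 + 2.1) = 16.0%, or 5.6 points.
- 12 to 15 cores, largest: 12 cores, 3 sectors, 70%, 15%. 2.1/(2.1 + 3.15) = 40.0% becomes 2.1/(2.1 + 1.35) = 60.9%, or 20.9 points.

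**Reading B: 12 regions, with a/p only a qualifier.** Assume 12 systematic cores (one per region, two of them in MRI-positive regions) plus 2 targeted cores, with 50% and 11% cancer rates in MRI-positive and MRI-negative regions. No region is missed, but each MRI-positive region enters twice, so r = 0.5.

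- By region: 2 × 0.5/(2 × 0.5 + 10 × 0.11) = 1.0/2.1 = 48%.
- By site: 4 × 0.5/(4 × 0.5 + 10 × 0.11) = 2.0/3.1 = 65%.

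The direction is the same, through a different mechanism.

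**The case against.** The strongest reply is that 24 sectors is an inference from a specimen label. No section makes those sectors a sampling frame or a denominator, and the stated unit is the biopsy site. That stands, and it is why both readings are worked. Under reading B nothing is unsampled, so weighting alone would change nothing; the fault is repeat counting.

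A reader might also infer several stronger things that the documents do not support:

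- *That at least 42% of sectors have no histology.* This needs one core to equal one sector, and it is 37.5% at 15 cores. A core could cross two sectors; section 6.1 locates tissue along the core.
- *That anterior sensitivity is 100% by construction.* The scheme of "12 labeled regions of the prostate including both medial and lateral locations from the base, mid, and apical regions" is background in section 1.2 on ultrasound-guided practice, not this trial's template. Section 1.4 attributes poor anterior access to the transrectal route, whereas this trial is transperineal and has an anterior label.
- *That every MRI finding is certain to be sampled.* Section 3.2 makes this a fair reading but does not state it. The direction needs only denser sampling of MRI-positive tissue.

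Materiality is also limited. Aim 1 in section 2.0 is confirmation of MRI targets, which is PPV. Section 10.1 calls the study hypothesis-generating, and section 9.2 anticipates no statistical analysis of effectiveness. In the illustration, 2.4 × 6 ≈ 14 cancer-positive sites give 50% with an exact 95% interval of about 23% to 77%, even ignoring clustering. Imprecision on that scale lowers the stakes but does not remove a systematic shift, and the plan still promises sensitivity and specificity for the MRI without limiting them to biopsied tissue.

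**Conclusion.** The point holds for whole-gland sensitivity and specificity. The stated estimator ignores a sampling scheme that depends on the MRI, so sensitivity is shifted up and specificity down under either reading of the site labels. This assumes that targeted cores make sampling of MRI-positive tissue denser, and that some cancer lies in MRI-negative tissue.

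The amount cannot be fixed from the documents. On the assumed grid and reading A it is about 7 to 16 points of sensitivity at 14 cores and about 6 to 21 points over 12 to 15 cores. PPV and NPV are not biased by unsampled MRI-negative sectors, provided the sampled ones are representative. As a description of the biopsied sites alone, the unweighted figures are what they say they are.

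**What to change.** In section 10.2:

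1. Make the prostate sector the unit and state how many there are. Give each sector one MRI status, fixed from the existing MRI before pathology is known, and one histology result, so that several cores in a sector count once. Add a rule for lesions and cores that span sectors.
2. Lead with PPV and NPV.
3. Report the fraction of MRI-negative sectors sampled. Report sensitivity and specificity with sampled MRI-negative sectors weighted by the inverse of that fraction, pooled over men (Begg-Greenes correction). State the assumption that sampled MRI-negative sectors represent unsampled ones. If 12 regions are chosen and all are sampled, the weight is 1 and step 1 does the work.
4. Describe any unweighted sensitivity or specificity as applying to biopsied sites only.

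Pooling is deliberate: weighting within man, or separately for anterior and posterior tissue, would leave very small cells with six men.

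The cost is analysis wording and a little extra work to record sector-level MRI status; no added cores, procedures or patients. The reported sensitivity will be lower and its interval wider. A fixed template does not guarantee that sampled MRI-negative sectors are representative, so that assumption should appear beside the result.

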3.3 Secondary Study Endpoints

3.3.1 We will report the post-operative radiation dose coverage for the prostate, organs at risk, and targeted lesion for each case. The coverage for the brachytherapy implant will be reported for the V100, V150, and V200, i.e. volumes of the prostate receiving 100, 150, and 200% of the prescribed dose. The dose delivered to the targeted lesion or lesions will be reported as a V100, V150, V200 as well to evaluate the ability to target the dose escalation prospectively, though again is per routine and not as part of a therapeutic trial design at this time. Additionally, the D90, i.e. dose to 90 percent of the prostate volume will be reported. Doses to the bladder, rectum and urethra will also be calculated for evaluation in the study.

3.3.2 An additional secondary endpoint for the study will be to report the incidence of successful completion of the transperineal biopsy procedure using the Uronav system which is provided by Philips Medical as part of the support for this study. The Symphony biopsy system will be available in the operating room (OR) as a back-up to complete the biopsies if needed. It is, however, anticipated that the combined DynaCAD computer for processing the MR images and Uronav systems supplied for the study to integrate with our standard transperineal ultrasound system will be 100% successful in obtaining the required biopsies. We will also report on any unanticipated complications or infections. It is anticipated that the risk of infection should be substantially diminished by avoiding transrectal biopsies. However, the risk for prostate edema and urinary obstruction may be increased due to the additional transperineal needle placement as the biopsy will be followed by routine prostate brachytherapy. Patients may therefore be asked to maintain a Foley catheter overnight to allow edema to resolve, and avoid acute obstruction the following day. Assuming the Uronav system is capable of completing biopsies on all patients and no more than 1 patient acquires a post-operative infection this pilot study will be deemed a success, and further investigation may be warranted.

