The goal for this pilot study is to show feasibility to track histopathology location correlated to standard and functional MR imaging with the possible implication to translate to a therapeutic trial design in subsequent studies to use the combined histopathology data and imaging correlation to direct radiotherapy using either brachytherapy or other forms of radiotherapy such as intensity modulated photon or proton therapy. Post-operative dosimetry will be reported for the whole gland as well as the targeted lesions per routine. The standard goal is to provide 150% of prescribed dose to the region defined as high probability for containing tumor at the time of the brachytherapy implant. As many patients do undergo a combination of both external beam radiation and brachytherapy as a boost dose, the implications could yield a secondary therapeutic trial in higher risk patients where the brachytherapy implant could be completed prior to the external beam therapy, and image guided intensity modulated radiotherapy (IMRT) could be designed to paint dose on the prostate gland following the implant to optimize target coverage. For example if the histopathology confirms cancer, but the post operative dosimetry defines a region that was not fully escalated to 150% of prescribed dose, one can envision using dose painting to target further dose to that region, or conversely if the implant post operative dosimetry shows high doses near any organ at risk such as the rectum or bladder, this area could be dose de-escalated in the additional 25 routine fractions of IMRT.

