4.2 Anticipated Number of Research Subjects

The pilot study is designed to include only 6 subjects for testing of feasibility to obtain transperineal tissues and report correlation to MRI image findings.

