10.0 Statistical Plan

10.1 Sample Size Determination

Sample size justification: This is a hypothesis-generating pilot study with enrollment of 6 patients. Each patient is expected to have 12 to 15 tissue samples using standard sextant biopsies in addition to targeted biopsies of intraprostatic MRI findings. Assuming 14 specimens are sent for histopathology analysis in 6 subjects we will use the 84 biopsy sites. Based on the report in the literature [6], we expect the cancer lesion detection rate of 22% using multiparametric MRI/US fusion vs. 11% under current standard care. Ignoring the potential correlation of multiple lesions from the same patient, 6 patients (84 lesions) will have 82% power to detect in 11% improvement of detection rate using 2-sided one-sample chi-square test with a significance level of 0.05.

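### Section 3.3.2 declares the whole pilot a success on biopsy completion and infection count alone, with no input from the primary endpoint or the stated goal

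*Combined protocol and SAP*

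**What the plan says.** Section 3.3.2, under secondary endpoints, introduces procedural completion in these terms: "An additional secondary endpoint for the study will be to report the incidence of successful completion of the transperineal biopsy procedure". The same subsection ends with a two-part rule. The first part is "Assuming the Uronav system is capable of completing biopsies on all patients"; the second part, with the verdict, is "no more than 1 patient acquires a post-operative infection this pilot study will be deemed a success, and further investigation may be warranted". The verdict is on the pilot study, not on the secondary endpoint alone.

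Section 3.2 states: "The primary endpoint will be to report correlation of biopsy tissue histopathology with intraprostatic MRI findings". Section 4.1 states: "The goal for this pilot study is to show feasibility to track histopathology location correlated to standard and functional MR imaging". It goes on to describe a possible later therapeutic trial that would use histology and imaging correlation to direct radiotherapy.

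Section 4.2 fixes the size: "The pilot study is designed to include only 6 subjects for testing of feasibility". Sections 10.3 and 11.8 contain safety stopping rules, which are not success criteria. Sections 9.2, 9.3, 10.1 and 10.2 attach no success criterion to the MRI-histology results.

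**The concern.** A success statement for a whole study should draw on what the study was set up to learn. Here the two inputs answer Specific Aim 2 (can Uronav guide transperineal biopsy?) and a safety question. Specific Aim 1, the primary endpoint and the goal in 4.1 all concern whether histology can be located and compared with MRI, and the rule is silent on that.

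What is at stake is what the pilot may conclude. Six completed procedures with at most one infection would earn the overall label even if cores were unreadable or could not be tied to an MRI location. A reader of the later report could then take the label as support for a therapeutic study that depends on that correlation.

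**Working it through.** **1. The plan's own design figure.** Section 10.1 gives 82% power for a two-sided one-sample chi-square test at 0.05. Its inputs are "Assuming 14 specimens are sent for histopathology analysis in 6 subjects we will use the 84 biopsy sites" and "we expect the cancer lesion detection rate of 22% using multiparametric MRI/US fusion vs. 11% under current standard care". With n = 14 × 6 = 84, p0 = 0.11 and p1 = 0.22:

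Power = Φ{[(p1 − p0)√n − 1.96√(p0(1 − p0))] / √(p1(1 − p1))} = Φ{[0.11 × 9.165 − 1.96 × 0.3129] / 0.4142} = Φ(0.953) = 0.830.

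This agrees with 82% to within about a point. It does not bear on the success rule: it concerns a detection rate, its result is not linked to 3.3.2, and 9.2 anticipates no statistical analysis of effectiveness.

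**2. What enters the rule.**

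| Quantity | Status in the protocol | In the 3.3.2 rule? |
|---|---|---|
| Uronav completion in all men | Secondary (3.3.2) | Yes |
| Post-operative infection, at most 1 man | Part of primary safety endpoint (3.4) | Yes |
| MRI-histology correlation | Primary (3.2) | No |
| Tracking of histology location against MRI | Goal (4.1) | No |
| Readable, location-matched cores | Collected (6.1), no criterion | No |

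**3. Does completion imply usable pairs?** Section 4.1 provides for virtual and gold fiducial tracking. Section 6.1 has each core labelled by location and PIRADS class, with the ends dyed or, at a minimum, the third of the biopsy cavity noted. But 3.3.2 describes completion only in terms of obtaining the biopsies. Matching also depends on core orientation and pathology processing after the needle procedure, and 6.1 sets no standard for an adequate match. A biopsy can be complete without yielding an evaluable pair.

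**4. Behaviour of the rule.** Let c be the completion probability and π the infection probability per man, independent across men and of each other. Then

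P(success) = c⁶ × [(1 − π)⁶ + 6π(1 − π)⁵].

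The documents expect c = 100% and give no value for π, so every π below, and every c below 100%, is an assumption.

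| c | π | P(success) |
|---|---|---|
| 100% | 1% | 0.999 |
| 100% | 5% | 0.967 |
| 100% | 10% | 0.886 |
| 100% | 20% | 0.655 |
| 100% | 30% | 0.420 |
| 98% | 5% | 0.886 × 0.967 = 0.857 |
| 95% | 5% | 0.711 |
| 90% | 5% | 0.514 |

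No MRI-histology quantity appears in the formula. That follows from the wording of the rule and needs none of the assumed rates.

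**5. Would a threshold help?** Assume one target per man. Zero of 6 positive targets has an exact 95% interval of 0% to 1 − 0.025^(1/6) = 46%; 6 of 6 has 54% to 100%. Six men are too few for a sharp PPV criterion. A rule that all six men be evaluable would be met with probability 0.95⁶ = 0.735 at an assumed 95% per man, taking 0.857 to 0.857 × 0.735 = 0.63.

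**The case against.** The best defence is that the sentence closes a paragraph on Uronav completion and infection, so it reads naturally as an Aim 2 verdict. It says only that further work may be warranted, and 4.1 treats the therapeutic trial as a possibility. No section makes 3.3.2 the formal trigger for that trial, so a reader who infers a binding go/no-go rule goes beyond the text. This part of the defence stands. It does not remove the problem, because the sentence passes judgement on the pilot as a whole.

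Second, most of what matching needs is already built into the procedure. MRI targets are transferred to Uronav, locations are tracked and cores are labelled. Every man must have a suspicious MRI lesion to enrol. This makes a complete absence of usable pairs less likely, and the documents give no rate for it. It does not define completion to include matching.

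Third, a reader might infer that the rule is defective because the pilot would pass even if every MRI target were benign. The documents do not support that reading. The primary endpoint is to report a correlation, 10.1 calls the study hypothesis-generating, and 9.2 anticipates no statistical analysis of effectiveness. Benign targets would be an informative result. Sections 3.2 and 10.2 require sensitivity, specificity and both predictive values to be reported, and 9.3 requires the biopsy result for each targeted lesion, so the verdict could not hide them.

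**Conclusion.** The point holds in limited form. The only overall success statement rests on one secondary and one safety outcome. It is independent of the primary endpoint and the stated goal, and completion is not defined so as to guarantee evaluable MRI-matched cores. The pilot could be declared a success without usable primary-endpoint data.

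This follows from the text alone. The probability of that outcome cannot be stated, because the documents give no rate for unreadable or unmatched cores. The success probabilities, including 0.857, rest on assumed completion and infection rates and on independence; they illustrate the rule and do not measure the harm. The primary analysis itself is unaffected. What changes is the conclusion that the pilot is entitled to draw, and the change is worth making because it is nearly free.

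**What to change.** Reword the end of 3.3.2 along these lines:

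> If Uronav completes the biopsies in all six men and at most one man has a post-operative infection, transperineal Uronav biopsy will be considered procedurally feasible with an acceptable infection count (Aim 2). Conclusions on Aim 1, and any recommendation for a therapeutic study based on histology-imaging correlation, will rest on the primary estimates with their intervals and on the number of men and cores with readable, location-matched histology, reported beside this statement.

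Add one line to 6.1 or 10.2 saying what counts as readable and location-matched, using the labelling already described in 6.1. State the interval method in 10.2; 10.1 already acknowledges possible correlation among lesions from the same patient.

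Do not add an all-men evaluability threshold or a PPV threshold. The first would make success materially harder to declare, and six men cannot support the second.

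Cost: a few sentences and two extra counts in the report. No new data are needed, since core location, PIRADS class and histology are already collected. The downside is a narrower success statement.
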